If there is an issue with capsule transit, will be monitored by investigator team and depending on location may exclude patient (i.e. if capsule transit delayed in stomach, would exclude patient based on exclusion criteria of gastroparesis). Patients with no bowel movement for 5 consecutive days, who are in need of a rescue treatment, will be instructed to contact the investigator. The following treatment is recommended, as applicable, in the following order:

- 1. Glycerin suppository
- 2. Enema
- 3. Laxadin/Bisacodyl tablets (3x5mg)

Administration of rescue treatment is at the discretion of the investigator based on an assessment of the subject; administration of rescue should be monitored and recorded.

3. Treatment Period (Day 0 to 22)

- a. **Day 0:** On the visit to initiate treatment, patients will return to the clinic to return their WMC monitor and be treated in a parallel-group design for 3 weeks. At this visit, the patient will return the SmartPill receiver and the study diary. Questions or concerns about the study will be discussed, including any changes in concomitant medications and new or worsening adverse events. If available, results of the SmartPill test will be reviewed by the patient's physician. If it is unclear that the capsule has passed, based on the subject's history or on the study results, erythromycin may be prescribed if the capsule is still in the stomach as a promotility medication or obtain an abdominal x-ray for verification to determine if the capsule is still in the colon. If the subject is female, then a urine pregnancy test will be performed before any abdominal xray. Issues with capsule transit will be addressed as above.

- b. Following the two-week run-in period, subjects will again complete the Rome IV Constipation module confirming that inclusion and exclusion criteria continue to be satisfied, and the patient will be randomized using the IWRS. The IWRS will notify the pharmacy to prepare the study drug (randomization output must only be seen by unblinded pharmacist).
- c. During 3-week treatment period, patients will ingest three capsules, twice daily, before breakfast and dinner (with 16 oz water).
- d. Patients will be asked to refrain from making any major lifestyle changes (e.g., starting a new diet or changing their exercise pattern) during the study.

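### A patient can be randomized on Day 0 before the baseline wireless motility capsule result is known to be evaluable, which puts primary-endpoint pairs at risk

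*Combined protocol and SAP*

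**What the plan says.** All references are to the combined protocol and SAP.

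- **Run-in (V.a.2).** The baseline capsule is taken on Day -7, and seven days are set aside for it to pass before treatment. Transit problems are monitored by the team, which may exclude a patient depending on where the capsule is. For delay in the stomach the text is firmer: the team "would exclude patient based on exclusion criteria of gastroparesis". No delay threshold is given. Prokinetic drugs are restricted during run-in unless the dose has been stable for three months.
- **Day 0, step a (V.a.3.a).** "At this visit, the patient will return the SmartPill receiver and the study diary". Then: "If available, results of the SmartPill test will be reviewed". The step foresees unclear passage. It mentions an abdominal x-ray for a capsule that may be in the colon, and says "erythromycin may be prescribed if the capsule is still in the stomach as a promotility medication". It closes by referring transit problems back to the run-in rule.
- **Day 0, step b (V.a.3.b).** The only check named before allocation is that "subjects will again complete the Rome IV Constipation module confirming that inclusion and exclusion criteria continue to be satisfied". Allocation comes directly after it, with no further condition: "and the patient will be randomized using the IWRS". The schedule of events (V.a.4) puts allocation on Day 0 and shows no window for that visit.
- **Analysis (V.c and VI.4).** CTT is the only primary endpoint. It is compared within patients, before and after, by a 3x2 repeated measures ANOVA, supported by a regression on change in transit time. The ITT population is everyone randomized and is primary for efficacy. There is no rule for a missing CTT.

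**The concern.** Both the ANOVA and the regression on change need a baseline CTT for each patient. Whether that baseline exists can be established before allocation, yet the plan does not require anyone to establish it. A patient whose trace has not been downloaded, or whose capsule has not clearly passed, can go on to randomization. The Rome IV constipation module is the only check named at that step, and a symptom questionnaire cannot show whether a CTT was recorded.

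Two things are at stake. Pairs for the primary endpoint may be lost after the slot has been used. And if the trace is read later and shows gastric delay, the team must either keep a patient whom the run-in text would exclude, or remove a randomized patient against the ITT definition.

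**Working it through.** **1. Is there a condition on randomization?** The Day 0 steps run in this order: receiver returned; result reviewed only if it is there; possible action for a retained capsule; transit problems referred to the run-in rule; Rome IV repeated; randomization. A gastric delay already known at this visit is caught before allocation by the reference back and by the criteria check in step b. An unread result is not caught, because no sentence makes randomization wait for it. Listed exclusion 30 covers a history of gastroparesis, not a WMC measurement.

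**2. Inputs for size.** From VI.4.c: a 10 h effect for carboxymethylcellulose (CMC), a further 3 h for CSP01 (1 h in the conservative case), SD 12 h and test-retest correlation 0.7. From III and IV.c: 45 subjects, 15 per arm. Assumed: placebo change 0 h, and alpha 0.05 (not in the readable text).

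**3. Reproducing the stated power.** The group-by-time test is a one-way ANOVA on change scores.

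- Variance of change = 12² × 2 × (1 − 0.7) = 86.4, so SD = 9.30 h.
- Changes 0/10/13 h: mean 7.667; sum of squared deviations = 58.78 + 5.44 + 28.44 = 92.67.
- Changes 0/10/11 h: mean 7; sum of squared deviations = 49 + 9 + 16 = 74.
- Noncentrality λ = (N/3) × sum of squares / 86.4; F test with 2 and N − 3 degrees of freedom.

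| Case | N | λ | Power | Stated |
|---|---|---|---|---|
| 3 h extra | 45 | 16.09 | 94.3% | 94% |
| 3 h extra | 30 | 10.73 | 79.8% | 80% |
| 1 h extra | 45 | 12.85 | 88.2% | 88% |

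All three stated figures reproduce. They presume 45 complete pairs.

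**4. Losing pairs.** The losses are assumed and spread evenly over the arms.

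| Pairs lost | N | Power, 3 h extra | Power, 1 h extra |
|---|---|---|---|
| 0 | 45 | 94.3% | 88.2% |
| 3 | 42 | 92.6% | 85.6% |
| 6 | 39 | 90.4% | 82.5% |
| 9 | 36 | 87.6% | 78.8% |

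**5. Is there slack?** 53 × 0.85 = 45.05. If 15% leave for other reasons, nothing remains for missing baselines. Section III does not define dropout, so the allowance may or may not be meant to cover them.

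**The case against.** The protocol is not silent. It sets aside seven days for passage, anticipates a retained capsule, and confirms the eligibility criteria before allocation. A reader might infer that a WMC-based exclusion can never act until after randomization. The documents do not support that: results may be in hand on Day 0, and a delay known then falls under the run-in rule. The problem is confined to results that are not available.

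A reader might also infer that erythromycin contaminates the baseline CTT. That is not supported either. The drug is mentioned at the visit where the receiver is returned, and nothing is recorded after that. The on-treatment measurement is a new test on Day 15.

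Nor is between-arm bias shown. Whether a baseline exists is settled before allocation, so its absence is unrelated to arm in expectation.

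Finally, the effect is modest. The trial is an exploratory pilot, and the protocol cites 80% power at 30 subjects as support for its sample size. In the table, only the largest assumed loss in the conservative case falls below 80%.

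These points limit the concern but do not remove it. The ITT label does not supply a missing baseline, and the plan names no method that would use a patient with only the on-treatment value.

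**Conclusion.** The point holds as a procedural gap that should be closed. As written, the plan permits randomization with the baseline WMC result unavailable or capsule passage unclear, and the paired primary analysis cannot use a patient without a baseline CTT. The stated power is not wrong; it depends on 45 complete pairs that the Day 0 procedure does not secure.

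Under the assumed losses, power falls by about 2 to 7 percentage points in the main case (94.3% to between 92.6% and 87.6%) and by about 3 to 9 in the 1-hour case (88.2% to between 85.6% and 78.8%). These figures rest on alpha 0.05, no change on placebo, the protocol's SD and correlation, and a loss rate that the documents do not give.

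Separately, the text on a capsule retained in the stomach is unresolved. The run-in passage leads to exclusion, while the Day 0 passage allows a promotility drug without saying whether the patient may then be randomized. One could infer that such patients are randomized, but the documents do not say so; giving the drug to a patient who is then excluded fits both passages. They must be reconciled with each other and with the run-in restriction on prokinetics.

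**What to change.** In V.a.3.b, make randomization in the web response system conditional on three confirmations: the receiver data have been downloaded, the baseline CTT is evaluable, and the WMC-based eligibility check is complete. State a window within which Day 0 may be postponed. Have the patient keep the receiver until capsule exit is recorded or the window ends.

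Reconcile the V.a.2 and V.a.3.a passages on a capsule retained in the stomach and the V.a.2 restriction on prokinetics, and state whether such a patient can be randomized. Which clinical rule applies is for the investigators to settle.

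The cost is protocol wording and a check in the randomization system. Some patients will wait or return once more. Postponement cannot rescue a trace that stays unevaluable, so those patients would not be randomized. That may remove some of the slowest-transit patients from a constipation trial. They could not have contributed to the paired primary analysis anyway, but the selection should be visible: report how many were not randomized for this reason.

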4. Patients reporting laxative, enema, and/or suppository usage for >2 days or any usage of a prohibited medication during the Run-in period
5. Patients reporting watery stools for any SBM (Type 7 on the Bristol Stool Form Scale [BSFS]) or loose (mushy) stools for >1 SBM (Type 6 on the BSFS) in the absence of laxatives during Run-in
6. GI motility obstruction or GI tract structural abnormality
7. Current use of prescribed or illicit opioids
8. History of pelvic floor dysfunction
9. Need for manual maneuvers in order to achieve a BM
10. History of GI lumen surgery at any time or other GI or abdominal operations within 60 days prior to entry into the study
11. History of high-dose stimulative or cathartic laxative abuse as judged by investigator team
12. Neurological disorders, metabolic disorders, or other significant disease that would impair their ability to participate in the study
13. Cardiovascular disease, diabetes, cancer, Crohn's disease, ulcerative colitis
14. BMI of <18.5 or >35 kg/m²
15. Pregnancy (or positive serum or urine pregnancy test(s) in females of childbearing potential) or lactation
16. Absence of contraception in females of childbearing potential
17. History of allergic reaction to carboxymethylcellulose, citric acid, sodium stearyl fumarate, raw cane sugar, gelatin, or titanium dioxide
18. Administration of investigational products within 1 month prior to Screening Visit
19. Exclusion of colonic inertia with symptoms of < 1 BM per 2 weeks
20. Subjects anticipating surgical intervention during the study
21. Known history of diabetes (type 1 or 2)
22. History of eating disorders including binge eating (except mild binge eater)
23. Supine SBP > 160 mm Hg and/or supine DBP > 95 mm Hg (mean of two consecutive readings)
24. Angina, coronary bypass, or myocardial infarction within 6 months prior to Screening Visit
25. History of swallowing disorders
26. Esophageal anatomic abnormalities (e.g., webs, diverticuli, rings)
27. History of gastric bypass or any other gastric surgery

28. History of small bowel resection (except if related to appendectomy)
29. History of gastric or duodenal ulcer
30. History of gastroparesis
31. History of abdominal radiation treatment
32. History of pancreatitis
33. History of intestinal stricture (e.g., Crohn's disease)
34. History of intestinal obstruction or subjects at high risk of intestinal obstruction including suspected small bowel adhesions
35. History of malabsorption
36. History of sucrose intolerance

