5. Randomization will be conducted via an interactive web-based response system (IWRS). Based on the randomized treatment assignment, an unblinded pharmacist at MGH will prepare the study treatment in a manner that ensures maintenance of the blind utilizing study-specific labels and completing details pertinent to the individual patient.
6. This is a double-blind study. The individual treatment assignment will not be revealed to patients or their representatives, study staff (except for the unblinded pharmacist), or the sponsor or the sponsor's representatives, until all patients complete the study and the database is locked. The unblinded pharmacist will maintain the treatment assignment for each patient.

V. Study Procedures

a.) Study visits and parameters to be measured

1. Eligibility Screen (Day -28 to -15)

- a. Vital signs, height, weight, and physical exam will be performed.
- b. Rome IV questionnaire to screen for CIC and IBS-C
- c. Blood sample collection (CBC, Chem 7, LFTs, Thyroid Hormone, ESR, and if applicable, serum pregnancy test)
- d. Urine sample for toxicity screening

2. Run-In Period (Day -14 to 0)

Day -14: After a screening visit in which patient eligibility will be determined through use of Rome IV constipation module along with other inclusion and exclusion criteria as above, there will be a two-week run-in period.

During this time no use of contraindicated medication per exclusion criteria or medications that may affect the bowel mobility will be allowed unless the subject has been on a stable dose for the last 3 months:

- a. Laxatives
- b. Prokinetic medications
- c. Anti-Depressant medications
- d. Medications for treatment of Parkinson disease
- e. Opiates
- f. Calcium-channel Blockers
- g. Aluminium/Magnesium
- h. Hydroxides
- i. Chronic use of non-steroidal anti-inflammatory drugs (NSAIDs) as defined by a frequency of at least 3 times a week for at least 6 months. Subjects on cardiac doses of aspirin may be enrolled in the study.

Day -7: Seven days into the run-in period, patients will undergo wireless motility capsule (WMC) testing to assess baseline motility. To allow for complete passing of the capsule, there will be a 7-day period following WMC ingestion prior to initiation of treatment to coincide with the end of the two-week run-in period.

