- e. Patients will be instructed to complete a simple, web-based daily diary using the Redcap system throughout the duration of the study which includes daily recording of number and time of bowel movements, complete/incomplete evacuation, and straining, abdominal discomfort, bloating, constipation severity, and overall relief using a nominal rating scale.
- f. **Day 1:** Subjects will begin taking study device. Patients will complete the Patient Assessment of Constipation Symptoms (PAC-SYM) and Quality of Life (PAC-QOL) to determine the severity of their constipation.
- g. **Day 15:** Following 14 days of treatment, patients will return to the clinic to undergo WMC testing to establish their motility profile on treatment and complete PAC-SYM, PAC-QOL questionnaires.
- h. **Day 22:** Following 21 days of treatment, patients will return to the clinic to return the WMC monitor and complete PAC-SYM, PAC-QOL questionnaires.
- i. **Day 31 (+3 days):** There will be a post-treatment period of 7 days during which time patients will continue to complete their daily diary. The clinical coordinator will call patients at the end of this follow-up period to ensure no adverse events occurred. After completion of the study, patients will be mailed the results of their SmartPill baseline test.

4. Schedule of Events

		Study						
		Run-in period			Treatment period			Post-treatment period
Time Point	Day -28 to -15	Day -14	Day -7	Day 0	Day 1	Day 15	Day 22	Day 31
Eligibility screen	X							
Informed consent	X							
Allocation				X				
CSP01 group				—————				
CMC group				◀	—————			▶
Placebo group				—————				
Rome IV questionnaire	X			X				
Daily diary		X	X	X	X	X	X	X
PAC-SYM		X		X	X	X	X	
PAC-QOL		X		X	X	X	X	
WMC testing			X			X		
Adverse events					X	X	X	X

5. There will be no routine monitoring of labs or imaging for the purposes of the study outside of usual care. Other study monitoring activities will be conducted as per Section IX of this protocol.
6. Patients enrolled in the study will not be allowed to be given standing laxative medications for prophylactic purposes, but rescue medications will be allowed on an as-needed (PRN) basis

b.) Investigational Product (IP) to be used

1. The IP will be supplied by the Sponsor and stored in the MGH inpatient pharmacy
 - a. CSP01 is supplied in capsule form (0.79 g per capsule, 2.37 g per dose)
 - b. CMC dose is supplied in capsule form (0.70 g per capsule, 2.1 g per dose)

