 - c. Matching placebo consists of an inert mixture supplied by the Sponsor in identical-appearing capsules
2. Rescue medications (in case of emergency)
 - a. If a subject experiences inadequate prevention of constipation while on the study treatment or placebo, the patient may be administered a rescue medication (laxative) at the discretion of the patient conferring with the Study physician or research NP consistent with “prn” orders or new orders from the medical team. Drugs that are available to treat constipation include: Colace (Docusate), Polyethylene glycol (Miralax), Senna (Senokot), magnesium citrate, and lactulose. Because constipation is not a side effect of the medication, all patients will be able to receive laxative doses as needed at their request throughout the study consistent with nurse’s or physician’s discretion without restriction.
 - b. Patients with no bowel movement for 5 consecutive days, who are in need of a rescue treatment, will be instructed to contact the investigator. The following treatment is recommended, as applicable, in the following order:
 - i. 1. Glycerin suppository
 - ii. 2. Enema
 - iii. 3. Laxadin/Bisacodyl tablets (3x5mg)
 - c. Administration of rescue treatment is at the discretion of the investigator based on an assessment of the subject; administration of rescue should be monitored and recorded.

c.) Data to be collected and timeline for collection

1. Primary endpoints
 - a. Colonic Transit Time (CTT)
2. Secondary endpoints
 - a. Spontaneous Bowel Movement (SBM) frequency rate
 - b. Complete Spontaneous Bowel Movement (CSBM) frequency rate
 - c. Stool consistency (Bristol Stool Form Scale)
 - d. Straining (Ease-of-Passage Scale)
 - e. Abdominal discomfort (Self Assessment on 0–10-point numerical rating scale)
 - f. Bloating (Self Assessment on 0–10-point numerical rating scale)
 - g. Constipation severity (Self Assessment on 0–10-point numerical rating scale)
 - h. Overall relief (Self Assessment on 0–10-point numerical rating scale)
 - i. Balloon Expulsion Time (BET) before and after
 - j. PAC-SYM change
 - k. PAC-QOL change
 - l. Need for rescue laxatives

c.) Adverse events

1. Definition of adverse events

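### Laxative, opiate and rescue passages need reconciling, the per-protocol set is written for inpatients, and laxative use is not linked to the colonic transit measurements

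*Combined protocol and SAP*

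**What the plan says.** **Entry.** Section III, exclusion 4, removes "Patients reporting laxative, enema, and/or suppository usage for >2 days or any usage of a prohibited medication during the Run-in period". Exclusion 7 removes "Current use of prescribed or illicit opioids", with no exception. Section V.a.2 (Run-In Period) lists drug classes that may not be used, among them laxatives and opiates, "unless the subject has been on a stable dose for the last 3 months". Section V.a, item 6, says that enrolled patients will "not be allowed to be given standing laxative medications for prophylactic purposes, but rescue medications will be allowed on an as-needed (PRN) basis".

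**Rescue.** Section V.b.2.a lets the patient, conferring with a study physician or research nurse practitioner, receive laxatives. It names five drugs and adds that "all patients will be able to receive laxative doses as needed at their request throughout the study consistent with nurse’s or physician’s discretion without restriction". Items 2b and 2c, and the matching text in V.a.2, tell patients with no bowel movement for 5 days who need rescue to contact the investigator. They recommend three other products in a set order, place administration at the investigator's discretion, and ask that "administration of rescue should be monitored and recorded".

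**Per-protocol set.** Section VI.4.a defines it by receipt of study medication on every day of hospitalization. The one violation it names is standing laxatives while hospitalized. Section IX.9.b takes the timing of daily doses from the hospital chart.

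**CTT measurement.** For the baseline capsule, swallowed on Day -7, "there will be a 7-day period following WMC ingestion prior to initiation of treatment". For the on-treatment capsule, on Day 15, "Following 14 days of treatment, patients will return to the clinic to undergo WMC testing", and the monitor comes back on Day 22. Section VI.4.b analyses CTT by a 3x2 repeated measures ANOVA, with a regression adjusting for IBS-C, balloon expulsion, age and sex. The need for rescue laxatives is a secondary endpoint (V.c.2).

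**The concern.** These passages govern who enters, what they may take during the study, and how the data are later sorted. Where they disagree, staff have opposite instructions and no stated order of precedence. A supplementary analysis set that refers to hospital days has nothing to act on in an outpatient trial.

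The link to the primary endpoint comes from the protocol itself: V.a.2 lists laxatives among drugs that may affect bowel motility. If a laxative is taken while the capsule is in the colon, the measured CTT may partly reflect the laxative. With 15 patients per arm, and with the stated hope in VI.4.c that the transit data will help set a threshold for future research, readers need to see how often this happened in each arm. The plan promises nothing that would show it.

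**Working it through.** No figure in the plan is disputed, so the check is mainly a comparison of passages.

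**1. Entry rules, applied to two patients.**

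- *Daily laxative at a dose stable for more than 3 months.* V.a.2 permits it. Exclusion 4 does not: daily use gives 14 days over the two-week run-in of V.a.2, or 7 days if one counts the 7-day baseline period of inclusion 5, and both exceed 2. Section V.a, item 6, adds to the tension, although its limit to prophylactic use leaves some doubt whether it covers existing stable treatment.
- *Opioid at a stable dose.* V.a.2 permits it. Exclusion 7 does not.

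Section V.a.3.b re-confirms the inclusion and exclusion criteria at Day 0, before randomization. Read alone, the exclusion criteria therefore still remove both patients. The stable-dose exception says the opposite for the same two drug classes.

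**2. Rescue rules, side by side.**

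- *Who decides.* Item 2a: the patient, on request and without restriction, yet also subject to nurse or physician discretion. Item 2c: the investigator.
- *When.* Item 2a: inadequate prevention of constipation on study treatment or placebo. Item 2b: contact the investigator after 5 days without a bowel movement.
- *What.* Item 2a: docusate, polyethylene glycol, senna, magnesium citrate, lactulose. Item 2b: glycerin suppository, enema, bisacodyl, in that order.

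The plain contradiction is over who decides, both within 2a and between 2a and 2c. The triggers and products could form two tiers, but the text does not say so.

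**3. Per-protocol set.** Patients come to clinic on Days 0, 15 and 22 and take capsules before breakfast and dinner for 3 weeks (V.a.3). No hospital stay is planned. Neither the dosing criterion nor the named violation can be evaluated, and there is no hospital chart from which to read doses.

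**4. Capsule windows.** Day -7 to Day 0 is 7 days; Day 15 to Day 22 is 7 days. Rescue is allowed in both. In the baseline window exclusion 4 limits use to at most 2 run-in days. In the on-treatment window no limit on days of as-needed use is stated, so exposure lies mainly there.

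**5. What is recorded.** Rescue is recorded (V.a.2, V.b.2.c), and concomitant medications carry start and end dates (IX.9.b). Dates show whether use fell in a capsule week. The diary items in V.a.3.e cover bowel movements and symptoms, not laxative use, and no clock time is requested. The secondary endpoint as written does not separate use inside the capsule windows from use outside them, and nothing in VI.4.b connects it to CTT.

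**6. The stated power.** With SD 12 h and correlation 0.7, the SD of change is 12 x sqrt(2 x (1 - 0.7)) = 9.295 h. For changes of 0, 10 and 13 h the mean is 7.667 and the squared deviations sum to 92.67, so the noncentrality at 15 per arm is 15 x 92.67 / 86.4 = 16.09 on 2 and 42 degrees of freedom. At an assumed alpha of 0.05 this gives 94.3%, against the stated 94%. The figure is reproduced. It contains no allowance for laxative use, and the documents supply nothing from which to compute one.

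**The case against.** Much can be said for the plan, and most of it stands.

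- A reader might infer that ineligible patients will be randomized. The text does not support that: eligibility criteria are cumulative, they are re-checked at Day 0, and exclusions 4 and 7 as written still apply. What remains is a conflict of instructions.
- A reader might infer that one route withholds rescue until 5 days have passed. It does not; it tells patients when to call, and earlier rescue is not barred. Nor do the different product lists contradict each other in themselves: one gives examples of available drugs, the other a recommended order.
- A reader might infer that rescue goes unrecorded. It is recorded and dated, and it is a secondary endpoint. Only the connection to CTT is missing.
- A reader might infer that the CTT comparison is biased or underpowered. That would need rates of laxative use by arm and an effect on CTT, and the documents give neither.
- The per-protocol set is optional and supplementary, so the main result does not depend on it.
- An as-observed intent-to-treat analysis is a legitimate primary analysis for an exploratory pilot. A model that censors CTT at laxative use would be imprecise at 15 per arm, and its censoring would be informative. It cannot be called a necessary part of the plan.

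None of this removes the conflict over the stable-dose exception, the contradiction over who decides on rescue, the hospitalization wording, or the absence of any report of laxative use by capsule window.

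**Conclusion.** The point holds in four limited parts. The run-in exception conflicts with exclusions 4 and 7, with no precedence stated. The rescue section contradicts itself on who decides. The per-protocol set cannot be built for outpatients. Laxative use during CTT measurement, mainly from Day 15 to Day 22, is permitted but not tied to the CTT result.

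The size and direction of any effect on the between-arm CTT contrast are unknown, and no loss of power is claimed. The conclusion assumes that no patient has a planned hospital stay, as the visit schedule indicates, and that laxatives can affect transit, as V.a.2 itself accepts. The changes should be made; the primary intent-to-treat analysis and the sample size stand.

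**What to change.** 1. Reconcile the exclusion criteria, the run-in drug list and its exception, both rescue passages (V.a.2 and V.b.2) and V.a item 6 into one consistent set of laxative, opiate and rescue rules, stating who decides. Which rule applies is for the clinical team.
2. Rewrite the per-protocol definition around the 3-week outpatient treatment period, and name an outpatient source for daily dosing in place of the hospital chart.
3. Add date and time of any laxative, enema or suppository to the daily diary.
4. Report laxative use by arm for each capsule window beside the CTT result.
5. Keep the as-observed intent-to-treat analysis of CTT as primary. Do not adjust for on-treatment laxative use, which arises after randomization. A supportive sensitivity analysis of CTT values measured under laxatives is optional; if done, state its imprecision and, if values are censored, that the censoring is informative.

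The cost is reconciled wording, one rewritten definition with a dosing source, one diary field with its small burden on patients, and one table.
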